Appendix 2 Criteria for Identifying Laboratory Values of Potential Clinical Relevance

Laboratory Tests		Criteria
Chemistry		
AST (SGOT)		$\geq 3 \times$ upper limit of normal (ULN)
ALT (SGPT)		$\geq 3 \times$ ULN
Alkaline phosphatase		$\geq 3 \times$ ULN
BUN		≥ 30 mg/dL
Creatinine		≥ 2.0 mg/dL
Uric Acid		
Men		≥ 10.5 mg/dL
Women		≥ 8.5 mg/dL
Bilirubin (total)		≥ 2.0 mg/dL
Creatine Phosphokinase (CPK)		$> 3 \times$ ULN
Hematology		
Hematocrit		
Men		$\leq 37\%$ and decrease of ≥ 3 percentage points from Baseline
Women		$\leq 32\%$ and decrease of ≥ 3 percentage points from Baseline
Hemoglobin		
Men		≤ 11.5 g/dL
Women		≤ 9.5 g/dL
White blood count		$\leq 2,800/\text{mm}^3$ or $\geq 16,000/\text{mm}^3$
Eosinophils		$\geq 10\%$
Neutrophils		$\leq 15\%$
Absolute neutrophil count		$\leq 1,500/\text{mm}^3$
Platelet count		$\leq 75,000/\text{mm}^3$ or $\geq 700,000/\text{mm}^3$
Urinalysis		
Protein		Increase of ≥ 2 units
Glucose		Increase of ≥ 2 units
Additional Criteria		
Chloride		≤ 90 mEq/L or ≥ 118 mEq/L
Potassium		≤ 2.5 mEq/L or ≥ 6.5 mEq/L
Sodium		≤ 126 mEq/L or ≥ 156 mEq/L
Calcium		≤ 8.2 mg/dL or ≥ 12 mg/dL
Glucose		
Fasting		≥ 100 mg/dL
Non-Fasting		≥ 200 mg/dL
Total Cholesterol, Fasting		≥ 240 mg/dL
LDL Cholesterol, Fasting		≥ 160 mg/dL
HDL Cholesterol, Fasting		
Men		< 40 mg/dL
Women		< 50 mg/dL
Triglycerides, Fasting		≥ 150 mg/dL

Protocol 405-201-00055 Statistical Analysis Plan

Appendix 3**Criteria for Identifying ECG Measurements of Potential Clinical Relevance**

Variable	Criterion Value ^a	Change Relative to Bas
Rate		
Tachycardia	≥ 120 bpm	increase of ≥ 15 bp
Bradycardia	≤ 50 bpm	decrease of ≥ 15 bp
Rhythm		
Sinus tachycardia ^b	≥ 120 bpm	increase of ≥ 15 bp
Sinus bradycardia ^c	≤ 50 bpm	decrease of ≥ 15 bp
Supraventricular premature beat	all	not present → prese
Ventricular premature beat	all	not present → prese
Supraventricular tachycardia	all	not present → prese
Ventricular tachycardia	all	not present → prese
Atrial fibrillation	all	not present → prese
Atrial flutter	all	not present → prese
Conduction		
1° atrioventricular block	PR ≥ 200 msec	increase of ≥ 50 ms
2° atrioventricular block	all	not present → prese
3° atrioventricular block	all	not present → prese
Left bundle-branch block	all	not present → prese
Right bundle-branch block	all	not present → prese
Pre-excitation syndrome	all	not present → prese
Other intraventricular conduction block ^d	QRS ≥ 120 msec	increase of ≥ 20 ms
Infarction		
Acute or subacute	all	not present → prese
Old	all	not present → prese ≥ 12 weeks post study
ST/T Morphological		
Myocardial Ischemia	all	not present → prese
Symmetrical T-wave inversion	all	not present → prese
Increase in QTc	QTcF > 450 msec (men) QTcF > 470 msec (women)	

^a In order to be identified as potentially clinically relevant, an on-treatment value must meet the “Criterion Value” and also represent a change from the subject’s baseline value of at least the magnitude shown in the “Change Relative to Baseline” column.

^b No current diagnosis of supraventricular tachycardia, ventricular tachycardia, atrial fibrillation, atrial flutter, or other rhythm abnormality.

^c No current diagnosis of atrial fibrillation, atrial flutter, or other rhythm abnormality.

^d No current diagnosis of left bundle branch block or right bundle branch block.

Protocol 405-201-00055 Statistical Analysis Plan

17 Proposed List of Summary Tables and Listings

Summary Clinical Tables:

CT-1.1 Subjects Disposition

CT-1.2 Subjects Disposition by Center

CT-1.3 Subject Completion Rates by Week (Enrolled Analysis Set)

CT-1.4 Enrollment By Country

CT-1.5 Enrollment By Country By Age Group

CT-2 Reasons for Discontinuation (Enrolled Analysis Set)

CT-3.1 Demographic Characteristics (Enrolled Analysis Set)

CT-3.2 Baseline Characteristics: Reasons to Smoke (Enrolled Analysis Set)

CT-3.3 Smoking History (Enrolled Analysis Set)

CT-3.4 Medical History (Enrolled Analysis Set)

CT-4.1 Concomitant Medications: Medications Taken Prior to Start of Study Therapy (Enrolled Analysis Set)

CT-4.2 Concomitant Medications: Medications Taken During Study (Enrolled Analysis Set)

CT-5.1.1.1 Smoking Continuous Abstinence Rate During Week 4-7 (Full Analysis Set)

CT-5.1.1.2 Smoking Continuous Abstinence Rate During Week 4-7 - Sensitivity Analysis I (Full Analysis Set)

CT-5.1.1.3 Smoking Continuous Abstinence Rate During Week 4-7 - Sensitivity Analysis II (Full Analysis Set)

CT-5.1.1.4 Smoking Continuous Abstinence Rate During Week 4-7 - Sensitivity Analysis III (Full Analysis Set)

CT-5.1.1.5 Smoking Continuous Abstinence Rate During Week 4-7-Using Only Exhaled Carbon Monoxide Level (Full Analysis Set)

[figure not shown]
CT-5.1.1.6 Smoking Continuous Abstinence Rate During Week 4-7 - Using Only Self-report (Full Analysis Set)

CT-5.1.2 Summary of Non-smoking Rate from Self-report and CO Level by Week (Full Analysis Set)

Protocol 405-201-00055 Statistical Analysis Plan

[figure not shown]
CT-5.1.3 Summary of Non-smoking Rate from Self-report by Week (Full Analysis Set)

CCI

Protocol 405-201-00055 Statistical Analysis Plan

CCI

CT-6.1.1 Expired Air CO breath Test Result (Full Analysis Set)

CT-6.1.2 Summary of Subjects with CO Level Greater Than or Equal to 5 PPM (Full Analysis Set)

CT-6.2 Summary of Change from Baseline in Average Number of Cigarettes Smoked Per Day by Week (Full Analysis Set)

CT-7.1 Extent of Exposure (Safety Analysis Set)

CT-7.2 Number and Percentage of Subjects Receiving Study Medication and Mean and Range of Average Daily Dose (Safety Analysis Set)

CT-8.1 Incidence of Adverse Events (All Causalities) (Safety Analysis Set)

Protocol 405-201-00055 Statistical Analysis Plan

CT-8.2.1 Incidence of Treatment-emergent Adverse Events by System Organ Class and MedDRA Preferred Term (Safety Analysis Set)

CT-8.2.2 Incidence of Treatment-emergent Adverse Events by System Organ Class, MedDRA Preferred Term and Severity (Safety Analysis Set)

CT-8.2.2.1 Incidence of Treatment-emergent Adverse Events Greater Than or Equal to 5% by System Organ Class and MedDRA Preferred Term (Safety Analysis Set)

CT-8.2.2.2 Incidence of non-Serious Treatment-emergent Adverse Events Greater Than or Equal to 5% by System Organ Class and MedDRA Preferred Term (Safety Analysis Set)

CT-8.2.3 Incidence of Treatment-emergent Adverse Events Greater Than or Equal to 2% by System Organ Class and MedDRA Preferred Term (Safety Analysis Set)

CT-8.2.4 Incidence and Occurrence (Number of Events) of Potentially Drug-Related Serious TEAEs by System Organ Class and MedDRA Preferred Term (Safety Analysis Set)

CT-8.2.5 Incidence and Occurrence (Number of Events) of Serious TEAEs by System Organ Class and MedDRA Preferred Term (Safety Analysis Set)

CT-8.2.6 Incidence and Occurrence (Number of Events) of Non-Serious TEAEs by System Organ Class and MedDRA Preferred Term (Safety Analysis Set)

CT-8.3.1 Incidence of Potentially Drug-related Treatment-emergent Adverse Events by System Organ Class and MedDRA Preferred Term (Safety Analysis Set)

CT-8.3.2 Incidence of Potentially Drug-related Treatment-emergent Adverse Events by System Organ Class, MedDRA Preferred Term and Severity (Safety Analysis Set)

CT-8.4.1 Incidence of Deaths Due to Treatment-emergent Adverse Events by System Organ Class and MedDRA Preferred Term (Safety Analysis Set)

CT-8.4.2 Incidence of Deaths Due to Treatment-emergent Adverse Events by System Organ Class and MedDRA Preferred Term and Severity (Safety Analysis Set)

CT-8.5.1 Incidence of Serious Treatment-emergent Adverse Events by System Organ Class and MedDRA Preferred Term (Safety Analysis Set)

CT-8.5.2 Incidence of Serious Treatment-emergent Adverse Events by System Organ Class, MedDRA Preferred Term and Severity (Safety Analysis Set)

Protocol 405-201-00055 Statistical Analysis Plan

CT-8.6.1 Incidence of Treatment-emergent Adverse Events Resulting in Discontinuations of Trial Medication by System Organ Class and MedDRA Preferred Term (Safety Analysis Set)

CT-8.6.2 Incidence of Treatment-emergent Adverse Events Resulting in Discontinuations of Trial Medication by System Organ Class, MedDRA Preferred Term and Severity (Safety Analysis Set)

CT-8.7.1 Incidence of Treatment-emergent Adverse Events of Special Interests by System Organ Class and MedDRA Preferred Term (Safety Analysis Set)

CT-8.7.2 Incidence of Treatment-emergent Adverse Events of Special Interests by System Organ Class and MedDRA Preferred Term and Severity (Safety Analysis Set)

CT-8.8.1 Incidence of Treatment-emergent Adverse Events related to Abuse-Potential by System Organ Class and MedDRA Preferred Term (Safety Analysis Set)

CT-8.8.2 Incidence of Treatment-emergent Adverse Events related to Abuse-Potential by System Organ Class and MedDRA Preferred Term and Severity (Safety Analysis Set)

CT-9.1 Listing of Deaths (Safety Analysis Set)

CT-9.2 Listing of Serious Adverse Events (Safety Analysis Set)

CT-9.3 Listing of Adverse Events Resulting in Discontinuations of IMP (Safety Analysis Set)

CT-9.4 Listing of Treatment-emergent Adverse Events of Special Interests (Safety Analysis Set)

CT-9.5 Listing of Treatment-emergent Adverse Events related to Abuse-Potential (Safety Analysis Set)

CT-10.1 Incidence of Laboratory Test Results of Potential Clinically Relevance (Safety Analysis Set)

CT-10.2.1 Laboratory Test Results for Chemistry - Mean Change from Baseline (Safety Analysis Set)

CT-10.2.2 Laboratory Test Results for Hematology - Mean Change from Baseline (Safety Analysis Set)

CT-10.2.3 Laboratory Test Results for Urinalysis - Mean Change from Baseline (Safety Analysis Set)

Protocol 405-201-00055 Statistical Analysis Plan

CT-10.2.4 Laboratory Test Results for Other Clinical Laboratory Tests - Mean Change from Baseline (Safety Analysis Set)

CT-10.2.5 Shift Tables of Clinical Laboratory Test Results - Chemistry (Safety Analysis Set)

CT-10.2.6 Shift Tables of Clinical Laboratory Test Results - Hematology (Safety Analysis Set)

CT-10.2.7 Shift Tables of Clinical Laboratory Test Results - Urinalysis (Safety Analysis Set)

CT-10.2.8 Shift Tables of Clinical Laboratory Test Results - Other Clinical Laboratory Tests (Safety Analysis Set)

CT-10.3.1 Listing of Laboratory Values of Potential Clinical Relevance by Subject (Safety Analysis Set)

CT-10.3.2 Listing of Laboratory Values of Potential Clinical Relevance by Test (Safety Analysis Set)

CT-10.5 Criteria for Laboratory Values of Potential Clinical Relevance

CT-10.6 Listing of Potential Hy's Law Cases by Subject (Safety Analysis Set)

CT-11.1 Incidence of Vital Signs of Potential Clinical Relevance (Safety Analysis Set)

CT-11.2 Vital Sign Parameters - Mean Change from Baseline (Safety Analysis Set)

CT-11.3 Listing of Vital Signs of Potential Clinical Relevance by Subject (Safety Analysis Set)

CT-11.4 Criteria for Potentially Clinically Relevant Vital Sign Abnormalities

CT-12.1 Incidence of ECG Measurements of Potential Clinical Relevance (Safety Analysis Set)

CT-12.2 ECG Parameters - Mean Change from Baseline (Safety Analysis Set)

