4.1 POINT OF ENROLLMENT

Participants will be enrolled at V2, after all safety laboratory results have been received and reviewed by the medical staff (MD or PA).

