5.2 DOSING REGIMEN

Centanafadine SR will be administered orally at a 400 mg TDD (200 mg BID) approximately 4 to 6 hours apart for a total of seven weeks. Doses of centanafadine SR can be taken without regard to meals and should be taken at approximately the same time each day, with the first dose taken in the morning. The second dose should be taken 4 to 6 hours after the first dose. If a subject forgets to take their second dose, they can take it up to 7 hours after their first dose; if they remember after 7 hours, they should skip the dose and resume dosing the next day.

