6.6.6 Final Study Visit (V6) – 7 weeks on IMP

Seven weeks (\pm 3 days) after starting the study drug, participants will return to the Center for V6 to complete questionnaires and assessments. Participants will also be asked to return all unused IMP.

The sequence of the following questionnaires and assessments will be at the discretion of the Investigator (or designee).

6.6.6.1 **Questionnaires**

- Other Nicotine Use Questionnaire
- Modified Shiffman-Jarvik Withdrawal Scale
- Modified Cigarette Evaluation Questionnaire Extended (mCEQE)
- Minnesota Withdrawal Questionnaire
- Fagerström Test for Nicotine Dependence

6.6.6.2 **Assessments**

- Review of Concomitant Medication
- Review of Concomitant Disease
- Expired air CO breath test
- Alcohol breath test
- Urine collection for urinalysis and pregnancy (all participants with the potential to become pregnant)
- Blood collection for safety laboratory testing, pharmacokinetics, and future biospecimen research (for those participants who consented to this optional collection)
- Vital signs (systolic and diastolic blood pressure, pulse rate, and respiratory rate), will be measured in sitting position after the participant has rested for at least 5 minutes.
- Weight
- Temperature
- Electrocardiogram (ECG) -- A standard 12-lead ECG will be recorded after the participant has rested for at least 5 minutes in a supine position.
- Columbia-Suicide Severity Rating Scale (C-SSRS)
- Review of adverse events (as needed)

- Physical examination (as needed)

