9.6 Electrocardiogram Data

A standard 12-lead ECG will be recorded after the participant has rested for at least 5 minutes in a supine position. The RR, PR interval, QRS duration, QT intervals, and QTc are recorded. The corrected QT intervals for QTcF are defined as follows:

QTcF is the length of the QT interval corrected for heart rate by Fredericia's formula:
$$QTcF = QT / (RR)^{1/3}$$

The potentially clinically relevant ECG abnormalities will be listed by subject. Criteria for potentially clinically relevant ECG abnormalities are provided in [Appendix 3](#). The incidences of abnormal ECGs of potentially clinical relevance based on the observation at the scheduled and the unscheduled post-baseline visits will be tabulated. Descriptive statistics of change from baseline in ECG intervals of PR, QRS, RR, QT, and QTcF at scheduled visits and last visit will be presented.

If ECG assessments are repeated for the same visit window, the last repeat values will be used for production of mean change from baseline. This is accomplished by sorting patient data by visit date and visit time (if applicable) within the same visit window.

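### SAP Appendix 3: the 12-week condition on an old infarction cannot be met by any in-window on-treatment ECG in this seven-week trial, so that single row is a structural zero (minor)

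*SAP*

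**What the plan says.** **Criterion.** In SAP Appendix 3, under Infarction, the Old row accepts any such finding as its criterion value. Its change column requires the finding to go from absent to present and adds "≥ 12 weeks post study". The right-hand edge of that column is cut off throughout the table in the extracted text, so the words after this point are not visible. The Acute or subacute row above it has no visible timing condition.

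**How the columns combine.** Footnote a reads "In order to be identified as potentially clinically relevant, an on-treatment value must meet the" criterion value and must also show the change given in the change column. The timing condition is therefore a requirement and not a remark.

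**Use.** SAP Section 9.6 applies these criteria to a by-subject listing and to an incidence table: "The incidences of abnormal ECGs of potentially clinical relevance based on the observation at the scheduled and the unscheduled post-baseline visits will be tabulated". The table is CT-12.1.

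**ECG schedule.** The Schedule of Events (Protocol Section 6.8) marks an ECG at V1 and V6 only. Protocol Section 6.6.6 times the last visit: "Seven weeks (\pm 3 days) after starting the study drug, participants will return to the Center for V6". Dosing runs "for a total of seven weeks" (Protocol Section 5.2). Contact after V6 is by telephone (Protocol Section 6.6.8).

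**The concern.** A 12-week condition sits in a trial with seven weeks of treatment and one scheduled ECG after baseline, at week 7. Take a participant whose V1 ECG shows no infarction and whose V6 ECG is read as an old one. The pattern is new since baseline. It fails the Old row on timing, and it fails the Acute or subacute row because of its label. It is therefore counted in neither infarction row.

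The zero printed in the Old row would look like an observed result, although the data could not have produced anything else. The protocol itself treats cardiac risk as material: exclusion 3 bars known ischaemic heart disease and prior infarction, and refers to sympathomimetic effects.

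**Working it through.** This is calendar arithmetic; no power or error-rate figure is involved.

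**Inputs**
- Threshold: 12 weeks = 12 × 7 = 84 days (SAP Appendix 3).
- Treatment: 7 weeks = 49 days (Protocol Section 5.2).
- V6 window: 49 ± 3 days after first dose (Protocol Section 6.6.6).
- Enrolment: "Participants will be enrolled at V2" (Protocol Section 4.1), with first dose one day after V2 (Protocol Section 6.6.2).
- V2: up to 28 days after V1 (Protocol Section 4.9.1). Protocol Section 3.1 gives a 14-day screening period instead. The longer window is used here because it is the more favourable to the criterion.
- Safety call: 7 to 10 days after V6 (Protocol Section 6.6.8).

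**The plan's own figure first.** Protocol Section 3.2 puts total participation at about 10 weeks. Screening + treatment + follow-up = 14 + 49 + 7 = 70 days = 10.0 weeks, which agrees. With 28-day screening, 28 + 49 + 7 = 84 days = 12.0 weeks. That total reaches the threshold only by including the telephone follow-up, when no ECG is scheduled.

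**Latest in-window V6 ECG, by time origin**

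| Origin | Days to latest V6 | Weeks | Short of 84 by |
|---|---|---|---|
| First dose | 49 + 3 = 52 | 7.4 | 32 days |
| Enrolment (V2) | 1 + 49 + 3 = 53 | 7.6 | 31 days |
| Screening (V1), 28-day window | 28 + 1 + 49 + 3 = 81 | 11.6 | 3 days |
| Screening (V1), 14-day window | 14 + 1 + 49 + 3 = 67 | 9.6 | 17 days |

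If the hidden words refer to the end of the study, the condition is further out of reach, since no on-treatment ECG follows the end of study.

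**Unscheduled ECGs.** SAP Section 9.6 includes these. The end of follow-up (V6 + 10 days) is at most 52 + 10 = 62 days from first dose, 53 + 10 = 63 from V2, and 81 + 10 = 91 from V1. Only the last exceeds 84. An ECG on day 84 from V1 after a full 28-day screening is 84 − 29 = 55 days after first dose, which is 55 − 49 = 6 days beyond the seven-week treatment period. Footnote a restricts counting to on-treatment values, so such an ECG would not qualify.

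**Size.** The Old row is 0 of 50 by construction. Each case that it would otherwise have shown is 1/50 = 2%.

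**The case against.** **The cell is truncated.** This stands as a caution. Reading it as time since study entry is an inference, and a qualifier may follow that cannot be seen. The timing result does not rest on the missing words, because it holds from first dose, enrolment, screening or end of study.

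**The row may be deliberate.** A waiting period could be meant to stop an infarct that pre-dated the study from being called new. On that view an inactive row is the right outcome in a short trial. The documents state no such purpose, and the absent-to-present requirement already removes infarcts seen at baseline.

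**A case would not be lost.** A reader might infer that CT-12.1 and the ECG listing are zero as a whole, or that a new infarction would disappear from the report. The documents support neither inference. The Acute or subacute, Myocardial Ischemia and Symmetrical T-wave inversion rows have no visible time limit and still feed both outputs. Protocol Section 9.2.1 has new clinically relevant abnormal findings documented as adverse events. SAP Section 9.2 treats an event starting after first dose as treatment-emergent. Protocol Section 6.5.7 sends ECG evaluations to the sponsor through the case report form. This part of the objection stands and limits the point to one row.

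**Labels are undefined.** Neither document says what separates acute, subacute and old. An infarct arising in seven weeks might be read as subacute and counted. That is fair: how often the gap would matter is unknown.

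**Never is too strong.** A V6 held three days beyond its window, after a full 28-day screening and counted from V1, reaches 81 + 3 = 84 days. Hence the claim is confined to in-window, on-treatment ECGs.

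**Conclusion.** The point holds for the Old infarction row alone, and it is minor. No on-treatment ECG within the planned windows can satisfy the 12-week condition. The nearest case is 3 days short, and it needs the most generous time origin and the latest permitted date at every step. The row is a structural zero in CT-12.1 and in the ECG listing.

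The conclusion assumes that the visible 12-week figure is complete and that no hidden qualifier waives it. It also gives the row the benefit of counting an in-window V6 ECG as on-treatment, a term that SAP Section 9.6 and Appendix 3 do not define.

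The number of participants affected cannot be estimated: the documents give no expected rate, and exclusion 3 should make such findings uncommon. The primary and secondary endpoints are untouched.

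The row looks like standard criteria not adapted to this trial. Appendix 2 likewise lists uric acid, creatine phosphokinase and lipids, which are not in the protocol's chemistry panel (Protocol Section 6.5.1). That supports treating the matter as a correction to the table and not as a gap in safety oversight.

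**What to change.** Check the full text of the cell in the source SAP. Then reconcile the row with this trial's ECG schedule by removing the 12-week condition for this trial. Any infarction pattern, whether acute, subacute or old, that is absent on the V1 ECG and present on a later on-treatment ECG should be tabulated in CT-12.1 and listed by subject.

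The cost is one table cell and one program condition, with no new data collection. The downside is an occasional flag for an infarct that pre-dated the study but was not read at V1; the listing would show each such case for review.

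Marking the row as not applicable would at least avoid a misleading zero, but it would still leave a pattern newly read as old outside the infarction rows.
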